* Discuss with Sponsor and Medical Monitor before implementing second dose level reduction. The rationale behind this dose reduction scheme is the steep relation between C_{max} and dose, e.g. the suggested 11% and 22% reductions in dose result in 19% and 33% lowering of the average C_{max}, respectively

All dose modifications, interruptions or discontinuations must be based on the worst preceding toxicity as graded by the NCI Clinical Toxicity Criteria (NCI-CTCAE version 5). Once a dose has been reduced during a treatment cycle, re-escalation during subsequent cycles may be permitted following discussion with the Medical Monitor. If the administration of

APR-246 is interrupted for reasons other than toxicity, then treatment with APR-246 may be resumed at the same dose. The same provision applies if the patient experienced an unacceptable toxicity not specifically described in Table 6, provided that this toxicity resolved to \leq Grade 1, unless otherwise specified.

Following 4 cycles of therapy for responding patients (i.e. CR, PR, HI, mCR with HI, mCR without HI) treatment with APR-246 and azacitidine can be delayed for up to 14 days to allow for count recovery at Investigator discretion pending discussion with the Sponsor and Medical Monitor.

Non-hematologic Grade 4 treatment related adverse events will lead to permanent discontinuation, irrespective of recovery time, unless otherwise specified. Exceptions would include nausea/vomiting/diarrhea which can be controlled by medications and/or asymptomatic electrolyte imbalances which can be corrected. In addition, in most instances, patients that experience a prolonged treatment interruption because of an adverse event and/or a Grade 3 adverse event will decrease the dose of study drug after their recovery (see specific tables for dose adjustment guidelines).

If any drug-related Grade 3 or 4 toxicity that is not clearly related to azacitidine is observed, APR-246 dose must be reduced for the next and subsequent cycles.

Patients requiring >2 dose reductions for APR-246 will be permanently discontinued from study drug. Patients who permanently discontinue APR-246 or azacitidine should have follow-up within 28 days after discontinuation of all study treatment or resolution of the AE to \leq Grade 1, whichever occurs first, that includes all study assessments appropriate to monitor the event.

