	Grade 2 (> 3.0 - 5.0 × ULN if baseline was normal; >3.0 - 5.0 × baseline if baseline was abnormal) in the absence of total bilirubin elevation to > 2.0 × ULN	Omit dose until resolved to ≤ Grade 1, then If resolved in ≤ 7 days, if first consecutive occurrence, then maintain dose level If second or more consecutive occurrence or if resolved in > 7 days, then ↓ 1 dose level
	Grade 3 (> 5.0 - 20.0 × ULN if baseline was normal; > 5.0 – 20.0 x baseline if baseline was abnormal) in the absence of total bilirubin elevation to > 2.0 × ULN	Omit dose until resolved to ≤ Grade 1, then If resolved in ≤ 7 days, if first consecutive occurrence, then maintain dose level. If second or more consecutive occurrence or if not resolved or resolved in > 7 days, evaluate if other contributing factors are present. If none, or after consideration of best interest of the patient, discontinue patient from APR-246. If other factors present consider continuing after ↓ 1 dose level
	Grade 4 (> 20.0 × ULN if baseline was normal; > 20.0 × baseline if baseline was abnormal)	Permanently discontinue patient from APR-246

◊ Please note that the Investigator is responsible for determining whether a patient meets potential Hy's Law (PHL) criteria at any point during the study. Hy's law identifies patients at risk for severe drug-induced liver injury, DILI, and is defined as AST or ALT ≥ 3× ULN together with Total Bilirubin Level ≥ 2×ULN, where no other reason, other than the suspected drug, can be found to explain the combination of increases, eg, elevated ALP indicating cholestasis, viral hepatitis, or another drug.

† Common Terminology Criteria for Adverse Events (CTCAE) version 5.

‡ For patients with Gilbert's syndrome, these dose modifications apply to changes in direct bilirubin only.

* LFTs include albumin, ALT, AST, total bilirubin (fractionated if total bilirubin > 2.0 × ULN), alkaline phosphatase.

Hematological Toxicities[†]

Parameter	Worst toxicity	Dose Modifications for APR-246
Febrile neutropenia	ANC < 0.5 × 10 ⁹ /L, temperature of ≥ 38 °C or a sustained temperature of ≥ 38°C for more than 1hour	Omit dose until resolved to ≤ Grade 1, then ↓ 1 dose level
Thrombocytopenia	Grade 4 (PLT < 25 × 10 ⁹ /L) [‡] and major bleeding event	Permanently discontinue patient from APR-246

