† Only applicable for patients with normal baseline absolute neutrophil count (ANC) and platelets. For patients with low (abnormal) baseline ANC and/or platelets that do not return to baseline (pre-cycle) after a clinically significant decrease following treatment, please contact the Medical Monitor.

‡ Common Terminology Criteria for Adverse Events (CTCAE) version 5.

Other Non-Hematological Toxicities

Parameter	Worst toxicity	Dose Modifications for APR-246
CNS – dizziness, dyskinesia and ataxia	Grade 1	Maintain dose level
	Grade 2	If resolved (to ≤ Grade 1) with medical therapy, continue same dose level If not resolved despite treatment interruption and maximal medical therapy, stop infusion and ↓ 1 dose level for subsequent dose
	Grade 3	Stop infusion and give medical therapy. If resolved (to ≤ Grade 1) with medical therapy, infusion may continue at the investigator’s discretion. ↓ 1 dose level for subsequent dose
	Grade 4	Permanently discontinue patient from APR-246.
Infusion Related Reaction	Grade 1	Maintain dose level.
	Grade 2	Maintain dose level; Symptomatic management (e.g., antihistamines, corticosteroids, narcotics, IV fluids)
	Grade 3	If resolved (to ≤ Grade 1) in < 4 hours with treatment interruption and medical therapy (e.g., antihistamines, corticosteroids, narcotics, IV fluids), continue same dose level and rate. If not resolved in < 4 hours despite treatment interruption and maximal medical therapy, stop infusion and ↓ 1 dose level for subsequent dose
	Grade 4	Permanently discontinue patient from APR-246.
Nausea/Vomiting/ Diarrhea	Grade 1	Maintain dose level
	Grade 2	If resolved (to ≤ Grade 1), then maintain dose level If not resolved despite maximal medical therapy, then ↓ 1 dose level
	Grade 3	If resolved (to ≤ Grade 1), then maintain dose level If not resolved despite maximal medical therapy, then ↓ 1 dose level
	Grade 4	Permanently discontinue patient from APR-246
Any Other Toxicity	Grade 3 or 4	Delay dose until resolution to ≤ Grade1, then ↓ 1 dose level

† Common Terminology Criteria for Adverse Events (CTCAE) version 5.

Treating physicians should use clinical judgment and may consult the Medical Monitor for guidance with dose modifications.

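### Section 6.2.1 and its own Table 6 prescribe different APR-246 actions for two resolved Grade 3 events, and disagree on whether controllable Grade 4 nausea, vomiting or diarrhea requires stopping

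*Combined protocol and SAP*

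**What the plan says.** All the competing instructions are in protocol Section 6.2.1, which introduces itself as setting out the rules for changing the APR-246 dose because of toxicity.

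**Running text, Grade 3 or 4.** "If any drug-related Grade 3 or 4 toxicity that is not clearly related to azacitidine is observed, APR-246 dose must be reduced". The same sentence fixes how long the reduction lasts: "APR-246 dose must be reduced for the next and subsequent cycles". The sentence just before it is softer: it says that in most cases a Grade 3 event or a prolonged interruption leads to a lower dose after recovery, and it points to the tables.

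**Table 6, Grade 3.**
- AST or ALT, without total bilirubin above 2.0 × ULN: "If resolved in ≤ 7 days, if first consecutive occurrence, then maintain dose level".
- Nausea/vomiting/diarrhea: "If resolved (to ≤ Grade 1), then maintain dose level".
- Infusion-related reaction resolving in under 4 hours: "continue same dose level and rate"; if it does not resolve in that time, "stop infusion and ↓ 1 dose level for subsequent dose".

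**Grade 4, non-hematologic.** The running text requires permanent discontinuation unless otherwise specified, then adds: "Exceptions would include nausea/vomiting/diarrhea which can be controlled by medications and/or asymptomatic electrolyte imbalances which can be corrected". The Table 6 row for Grade 4 nausea/vomiting/diarrhea reads only: "Permanently discontinue patient from APR-246".

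**Status of the table.** Table 6 is titled as recommendations for treatment-related adverse events. It closes by leaving room for clinical judgment and optional consultation with the Medical Monitor.

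**The concern.** The running-text sentence and Table 6 cover the same kind of event, one related to treatment, yet they give opposite instructions for some Grade 3 events. A site that keeps the dose follows the table row and departs from a mandatory sentence. A site that reduces follows the sentence and departs from the row.

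Four things depend on this:

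- **Exposure.** APR-246 dosing can differ between sites for the same event. These rules apply only to the experimental arm.
- **Remaining reductions.** Section 6.2.1 requires discussion with the Sponsor and Medical Monitor before a second reduction, and permanent discontinuation if more than two are needed. Whether a site reduces after one of these events changes how many reductions that patient has left.
- **Deviations.** Section 5.5 requires protocol deviations to be recorded in the CRF and/or monitoring reports. The text does not settle whether keeping the dose is a deviation.
- **Safety reporting.** Section 9.3.3 summarizes adverse events leading to early discontinuation of study drug. The Grade 4 disagreement can shift that count by site.

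**Working it through.** The main check is a row-by-row comparison of Table 6 with the running text, for treatment-related events not clearly due to azacitidine. The plan has no figure of its own to reproduce here.

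**Grade 3.** Running-text rule: reduce for the next and later cycles.

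| Table 6 parameter | Table 6 action at Grade 3 | Against the running text |
|---|---|---|
| Serum creatinine | One level down after resolution | Agrees |
| Bilirubin | One level down after resolution (re-escalation may be considered) | Agrees on the reduction |
| AST or ALT | Dose kept if a first event resolves in ≤ 7 days | Conflicts |
| CNS | One level down for the subsequent dose | Agrees |
| Infusion reaction | Same dose level and rate if resolved in < 4 hours | Probable conflict |
| Nausea/vomiting/diarrhea | Dose kept if resolved to ≤ Grade 1 | Conflicts |
| Any other toxicity | One level down after resolution | Agrees |

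Firm conflicts: 2/7 = 28.6%. With the probable row: 3/7 = 42.9%. Already reducing: 4/7 = 57.1%. These are shares of table rows, not of patients or events. The two hematological rows are set up differently and are not counted.

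The infusion-reaction row is only probable. Its two branches contrast the infusion under way with the subsequent dose, so it can be read as governing only the infusion in progress.

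**Grade 4, non-hematologic, same seven parameters.** Five rows (creatinine, bilirubin, AST/ALT, CNS, infusion reaction) order permanent discontinuation and match the general rule. Nausea/vomiting/diarrhea disagrees with the text's exemption. A site that stops breaches neither passage, so the disagreement is over whether stopping is required. The exemption names no dose, and the mandatory-reduction sentence also covers Grade 4, which adds a third reading: continue one level lower.

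The seventh row, any other toxicity, is ambiguous rather than contradictory. It reduces one level after resolution. The general Grade 4 rule stops permanently. Another sentence lets toxicities not described in Table 6 resume at the same dose once resolved to Grade 1 or less. Both of those last two carry an unless-otherwise-specified clause, and nothing says whether this row is the case meant.

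**Size of one dose step.** Inputs from Table 5: starting level 4.5 g/day (1.5 g + 3.0 g); first reduction 4.0 g/day (1.33 g + 2.67 g = 4.0 g).

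- Daily dose: (4.5 − 4.0)/4.5 = 11.1%
- First 45 minutes: (1.5 − 1.33)/1.5 = 11.3%
- Next 5 h 15 min: (3.0 − 2.67)/3.0 = 11.0%
- Four-day course: 4 × 4.5 = 18 g against 4 × 4.0 = 16 g

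The note to Table 5 equates the 11% step to a 19% lower average Cmax.

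**The case against.** The best defense is that the text already expects exceptions. The softer sentence says most instances and refers to the tables, Table 6 calls itself recommendations, and re-escalation in later cycles is allowed after discussion with the Medical Monitor. On this view the table refines the text. This does not remove the conflict: the mandatory-reduction sentence stands alone, applies to any such toxicity, and neither defers to the tables nor excepts resolved events. Re-escalation does limit how long an 11% difference need last. If the table is merely advisory, the mandatory sentence overrides it and its two dose-keeping rows cannot be followed for these events.

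A second argument is that the nausea/vomiting/diarrhea row might govern only the remaining infusion days of the same cycle, with the reduction starting in the next. This is possible but strained. The alternative action in the same row, one level down, carries no such limit, and the row lacks the contrast seen in the infusion-reaction row. AST/ALT is the clearer of the two conflicts.

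Three limits stand. If Table 6 is only advisory, a site that reduces is hard to call deviant, so the deviation question bears mainly on sites that keep the dose. The affected set is narrow: events clearly due to azacitidine are excluded, and the AST/ALT conflict needs a first event, resolution within 7 days and no bilirubin above 2.0 × ULN. The documents give no frequency for any of these events.

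**Conclusion.** The inconsistency is real and should be fixed. For two resolved Grade 3 events, AST/ALT and nausea/vomiting/diarrhea, the mandatory sentence and Table 6 cannot both be followed. The infusion-reaction row is a probable third. For Grade 4 nausea/vomiting/diarrhea controllable by medication, the text and the table disagree on whether permanent discontinuation is required.

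At the starting dose the Grade 3 disagreement is worth one level: 4.5 g against 4.0 g per day, or 18 g against 16 g per course. The conclusion assumes that the event is treatment-related, is not clearly due to azacitidine, and resolves as the row specifies. No effect on the complete remission comparison, power or type I error is shown. The consequence is site-dependent dosing, deviation coding and discontinuation counts in the experimental arm.

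**What to change.** Issue a protocol clarification amendment that reconciles the running text of Section 6.2.1 with Table 6, so that each event and grade leads to one action. It should:

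1. State which text governs where they differ, and whether Table 6 is binding or advisory.
2. Reconcile the mandatory-reduction sentence with the Grade 3 AST/ALT and nausea/vomiting/diarrhea rows.
3. Say whether the Grade 3 infusion-reaction row covers only the infusion in progress.
4. Reconcile the Grade 4 nausea/vomiting/diarrhea exemption with its row and, if treatment may continue, make the dose instruction explicit.
5. Say whether the any-other-toxicity row is an otherwise-specified case of the Grade 4 rule and of the same-dose resumption sentence.
6. Align Section 6.2.2, which names nausea as a possible CNS event and only recommends reduction after Grade 3 or higher CNS events.

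The sponsor's clinical team chooses the rules; this review takes no position on them. The cost is one clarification amendment, with no added procedures or patients.

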Table 6. Recommendations for APR-246 Dose Modifications and Criteria for Treatment Interruption and Re-Initiation with Treatment-Related Adverse Events

Any changes in dose must be recorded on the Dosage Administration Record CRF.

Renal Toxicities

Parameter	Worst toxicity [†]	Dose Modifications for APR-246
Serum Creatinine	Grade 1 (< 1.5 × baseline)	Maintain dose level
	Grade 2 (> 1.5 to 3.0 × baseline)	Omit dose until resolved to ≤ Grade 1, then: If first occurrence, then maintain dose level If second or more consecutive occurrence, then ↓ 1 dose level
	Grade 3 (> 3.0 – 6.0 × baseline)	Omit dose until resolved to ≤ Grade 1, then: ↓ 1 dose level If not resolved or resolved in > 7 days, evaluate if other contributing factors are present. If none, or after consideration of best interest of the patient, discontinue patient from APR-246. If other factors present, consider continuing after ↓ 1 dose level
	Grade 4 (> 6.0 × baseline)	Permanently discontinue patient from APR-246
† Common Terminology Criteria for Adverse Events (CTCAE) version 5.		

Hepatic Toxicities[◇]

Parameter	Worst toxicity	Dose Modifications for APR-246
Bilirubin [‡]	Grade 1 (> ULN - 1.5 × ULN)	Maintain dose level with LFTs [‡] monitored as per protocol
	Grade 2 (> 1.5 - 3.0 × ULN) with ALT or AST ≤ 3.0 × ULN	Omit dose until resolved to ≤ Grade 1, then: If resolved in ≤ 7 days, if first occurrence, then maintain dose level If second or more consecutive occurrence or if resolved in > 7 days, then ↓ 1 dose level
	Grade 3 (> 3.0 - 10.0 × ULN) with ALT or AST ≤ 3.0 × ULN	Omit dose until resolved to ≤ Grade 1, then: If resolved in ≤ 7 days, ↓ 1 dose level. If no subsequent event, consider re-escalation to original dose level. Omit dose until resolved to ≤ Grade 1, then: ↓ 1 dose level. If second or more consecutive occurrence or if not resolved or resolved in > 7 days, evaluate if other contributing factors are present. If none, or after consideration of best interest of the patient, discontinue patient from APR-246. If other factors present, consider continuing after ↓ 1 dose level.
	Grade 4 (> 10.0 × ULN)	Permanently discontinue patient from APR-246

Parameter	Worst toxicity	Dose Modifications for APR-246
AST or ALT	Grade 1 (> ULN - 3.0 × ULN if baseline was normal; 1.5 - 3.0 × baseline if baseline was abnormal)	Maintain dose level with LFTs [‡] monitored per protocol

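### Table 6 orders no APR-246 hold when AST, ALT and bilirubin rise together at Grade 2, although an isolated Grade 2 rise in either requires one

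*Combined protocol and SAP*

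**What the plan says.** All of this is in Section 6.2.1 and its Table 6.

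- **Bilirubin rows, Grades 2 and 3.** They apply only "with ALT or AST ≤ 3.0 × ULN".
- **AST/ALT rows, Grades 2 and 3.** They apply only "in the absence of total bilirubin elevation to > 2.0 × ULN".
- **Action for an isolated Grade 2 rise, either kind.** APR-246 is withheld until the value is back to Grade 1 or below. A first event that clears within 7 days returns to the same dose. Otherwise: "If second or more consecutive occurrence or if resolved in > 7 days, then ↓ 1 dose level".
- **Isolated Grade 3 rows.** For slow or absent resolution, or a consecutive recurrence, other causes must be looked for. "If none, or after consideration of best interest of the patient, discontinue patient from APR-246".
- **Hy's Law footnote.** The pattern "is defined as AST or ALT ≥ 3× ULN together with Total Bilirubin Level ≥ 2×ULN", with no other explanation. The footnote says that it marks risk of severe drug-induced liver injury and makes the investigator responsible for recognising it. It attaches no hold, stop or work-up.
- **Catch-all row.** Grade 3 or 4 only: delay until Grade 1 or below, then one level down.
- **General text.** "All dose modifications, interruptions or discontinuations must be based on the worst preceding toxicity". Drug-related Grade 3 or 4 toxicity not clearly due to azacitidine requires a reduction. "Patients requiring >2 dose reductions for APR-246 will be permanently discontinued from study drug". A toxicity that Table 6 does not describe may be followed by dosing at the same level once it is back to Grade 1 or below.

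**The concern.** The two exclusions (enzymes at or below 3.0, bilirubin not above 2.0) sit at the Hy's Law thresholds in the footnote. They look intended to lift the combined pattern out of the single-value rows so that it can be handled separately, but the table has no row to receive it. At Grade 2 + Grade 2, the pattern that the protocol flags for severe liver injury therefore carries a weaker written instruction than either of its components.

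The stake is patient safety in the experimental arm. Chemistry is drawn before Day 1 of each cycle, and APR-246 is given on Days 1 to 4. A patient who shows this pattern on Day 1 has no written hold. Section 2.8.1 also notes, from mouse data, a possible effect on acetaminophen glucuronidation, though no resulting case of hepatotoxicity has been identified.

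**Working it through.** No published figure needs reproducing; the check is of the rules. Values are multiples of ULN, with a normal baseline unless stated.

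**Inputs (Table 6).** Bilirubin: Grade 2 is >1.5 to 3.0, Grade 3 is >3.0 to 10.0, Grade 4 is >10.0. AST/ALT: Grade 2 is >3.0 to 5.0, Grade 3 is >5.0 to 20.0, Grade 4 is >20.0. Grade 4 rows carry no condition.

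**Step 1: when both sets of rows close.** Reading the text literally, the Grade 2 and 3 bilirubin rows close when AST and ALT are both >3.0. The Grade 2 and 3 AST/ALT rows close when bilirubin is >2.0. Both sets are closed when all three conditions hold.

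**Step 2: worked cases.**

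| AST = ALT | Bilirubin | Result |
|---|---|---|
| 1 | 2.5 | Bilirubin Grade 2 row: hold |
| 4 | 1 | AST/ALT Grade 2 row: hold |
| 4 | 1.8 | AST/ALT Grade 2 row: hold |
| 4 | 2.5 | Grade 2 + Grade 2: no hepatic row, catch-all not reached |
| 4 / 10 / 10 | 5 / 2.5 / 5 | Catch-all: delay, one level down |
| 4 / 10 / 25 / 25 / 25 | 12 / 12 / 2.5 / 5 / 12 | Grade 4 row: permanent discontinuation |

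With Grade 2 bilirubin taken in its >2.0 to 3.0 part, there are 3 × 3 = 9 combinations of Grades 2 to 4. One has no ordered action, three go to the catch-all and five stop: 1 + 3 + 5 = 9. These are table cells, not patients.

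**Step 3: the three Grade 3 combinations.** On Table 6 alone, a first isolated AST/ALT Grade 3 event that clears in 7 days or less resumes at the same dose, so the catch-all is stricter for that case. For slow resolution or a consecutive recurrence, the isolated rows call for a cause evaluation and possible discontinuation. The catch-all gives only another reduction: 4.5 g to 4.0 g, then 3.5 g (after discussion with the Sponsor and Medical Monitor), then a stop, because a third reduction exceeds two. This assumes no reductions for other reasons and that re-escalation does not reset the count.

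**Step 4: abnormal AST/ALT baseline.** Section 5.1 admits AST/ALT below 2.5 × ULN, or higher if due to MDS. The Grade 1 limit is then 3.0 × baseline:

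- baseline 1.5: 3.0 × 1.5 = 4.5 × ULN
- baseline 2.0: 3.0 × 2.0 = 6.0 × ULN
- baseline 2.4: 3.0 × 2.4 = 7.2 × ULN

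Take baseline 2.0, AST = ALT = 4 and bilirubin 2.5. The enzymes are at 4 / 2.0 = 2.0 × baseline, which is Grade 1, and that row maintains the dose. Bilirubin is Grade 2, but its row is closed because both enzymes exceed 3.0 × ULN. The worst-toxicity sentence points to Grade 2, for which no open row gives an action.

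**The case against.** The best case for the current text has four parts.

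**Judgement covers it.** The synopsis says that treatment must stop for an adverse experience that the investigator judges an unacceptable risk. Section 5.4 provides for stopping on toxicity. Table 6 is titled as recommendations for treatment-related events and closes by inviting clinical judgement and optional Medical Monitor consultation. The footnote draws attention to exactly this pattern. All true, but these provisions permit a hold and do not order one. The protocol did not leave isolated Grade 2 rises to judgement.

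**The same-dose sentence covers it.** If the provision for toxicities not described in Table 6 applies, dosing resumes only at Grade 1 or below. That is close to the result for a first isolated Grade 2 event. But it sets a condition for resuming and does not order the interruption. It has no 7-day test and no recurrence rule.

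**Grade 3 combinations are covered.** A reader might infer that they are unprotected. They are not: the catch-all delays and reduces, an unresolved event is not redosed, and the general reduction rule also applies. Only the evaluate-and-discontinue step is lost, and that step is itself conditional. This part of the objection stands.

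**The gap is narrow.** It is one combination, and APR-246 is given on 4 days of 28, so a hold matters mainly if the pattern persists to, or appears at, the start of a cycle. This also stands.

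Three further readings go too far. The text does not tell investigators to keep dosing through a Hy's Law pattern: at Grade 2 + Grade 2 it is silent, and with an abnormal baseline it is ambiguous. A rise in only one enzyme is not part of the gap, because on the literal wording the bilirubin hold still applies. Nor can one say that the trial has no Hy's Law procedure, since the detailed safety plan and the Investigator's Brochure are not among these documents.

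**Conclusion.** The point holds for one combination. With a normal baseline, AST and ALT both >3.0 to 5.0 × ULN and total bilirubin >2.0 to 3.0 × ULN, the protocol orders no APR-246 hold, although either rise alone at Grade 2 requires one. This follows from stated conditions in the table, not from missing detail, and it should be corrected.

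Two secondary points are weaker: the evaluate-and-discontinue step lost for three Grade 3 combinations, and the unclear instruction for patients with an abnormal AST/ALT baseline.

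The conclusion rests on reading the row conditions literally and on the protocol text alone. The documents give no frequency for the pattern, so no number of affected patients can be offered. The primary comparison of CR rates is unaffected.

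**What to change.** Add one row to Table 6.

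- **Trigger.** AST or ALT ≥ 3 × ULN with total bilirubin ≥ 2 × ULN. Use direct bilirubin in Gilbert's syndrome, in keeping with the existing footnote that "these dose modifications apply to changes in direct bilirubin only". For a value already raised at entry, also require a rise above the patient's own baseline, with the size set by the sponsor's safety physicians.
- **Action.** Hold APR-246 until Grade 1 or below, or baseline if that was abnormal. Evaluate other causes. Then discontinue, or resume no higher than one level down, in line with the evaluate-and-stop step in the Grade 3 rows. The safety physicians should decide whether finding no other cause means a mandatory permanent stop; the documents do not settle that.
- **Precedence.** The new row overrides the other Grade 1 to 3 hepatic rows and the same-dose sentence. Grade 4 stays permanent discontinuation.
- **Exclusions.** Replace both with a condition that the combined row is not met. This also removes the unclear wording about ALT or AST.

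The baseline condition and the reworded exclusions belong together. Without the first, the row would fire at unchanged entry values of 3.2 (enzymes) and 2.2 (bilirubin) × ULN, which the exceptions in Section 5.1 can admit. Without the second, entry bilirubin of 2.2, unchanged, with enzymes rising from normal to 4 × ULN would still match no row. With both, that patient gets the AST/ALT Grade 2 hold.

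The cost is an amendment of one row, one precedence sentence and edited row conditions. AST, ALT, alkaline phosphatase and total bilirubin are already drawn weekly until CR and at least on Day 1 of each cycle afterwards, and bilirubin is already fractionated above 2.0 × ULN. A few patients will be held or stopped earlier, some for bilirubin rises later attributed to MDS, hemolysis or transfusion. An occasional cause work-up will be needed, such as hepatitis serology, which is not mandatory at entry.

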Psychiatric				
Confusional state	2 [1 SAE] [1 DLT]	1	1	
Dysphemia	[1 DLT]			
Hallucination	[1 DLT]			
Bradyphrenia			1	
Disorientation		1		
General				
Fatigue	5	4	22	29
Gait disturbance			1	

Nausea and vomiting may also be triggered from the CNS, but are not listed in this overview. From the category General disorders and administration site conditions, only fatigue and gait disturbance are listed, being potentially CNS-related. Other AEs reported in this category were pyrexia, edema, mucosal inflammation, malaise, death and disease progression.

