6.2.2 Management of CNS Adverse Events

If a patient reports any clinical adverse event of any grade during the administration period of APR-246 that could be considered to originate from the CNS (e.g. dizziness, vertigo, nausea) then the patient will be given a rescue medication as per the institutional standard of care.

Dose modifications have been successfully used to manage potential CNS effects occurring during the infusion. For any clinical adverse event Grade ≥ 3 , the infusion should immediately be stopped, and if all symptoms resolve to CTCAE \leq Grade 1 within 2 hours, the infusion may be resumed at the same infusion rate. If the same symptoms do occur or increase in severity during re-challenge the infusion should be stopped.

If the event lasts longer than 2 hours, then the APR-246 infusion should be discontinued for that day, the remaining drug should be discarded, and toxicity should be managed according to recommendations in Table 6.

After an adverse event considered as related, a single level dose reduction of APR-246 is allowed. Dose reduction is recommended after any Grade ≥ 3 CNS AEs.

In prior studies, prochlorperazine 10 mg orally tid (three times daily) has been reported to be an effective treatment that may also be used prophylactically. When prochlorperazine is used prophylactically, start the day prior to the Day 1 and continue 10 mg tid to day 4 (as needed). The US label for prochlorperazine does not list QT prolongation as a known risk associated with use of this drug.

Re-escalation after dose reduction due to any APR-246-related toxicity may be permitted following discussion with the Medical Monitor.

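### Section 6.2.1 and Table 6 disagree on whether APR-246 stops or restarts after a related non-haematologic Grade 4 toxicity without its own row, and no order of precedence is stated

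*Combined protocol and SAP*

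**What the plan says.** All the main instructions are in protocol section 6.2.1.

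- **Stop rule (text):** "Non-hematologic Grade 4 treatment related adverse events will lead to permanent discontinuation, irrespective of recovery time, unless otherwise specified".
- **Exceptions (text, next sentence):** "Exceptions would include nausea/vomiting/diarrhea which can be controlled by medications and/or asymptomatic electrolyte imbalances which can be corrected".
- **Last row of Table 6** (Other Non-Hematological Toxicities, any other toxicity, Grade 3 or 4): "Delay dose until resolution to ≤ Grade1, then ↓ 1 dose level".
- **Reduction sentence (text):** after any drug-related Grade 3 or 4 toxicity not clearly due to azacitidine, the APR-246 dose has to be lowered from the next cycle on.
- **Same-dose sentence (text):** an unacceptable toxicity that Table 6 does not specifically describe may be followed by resumption at the same dose once it is Grade 1 or less, again with a proviso for cases specified elsewhere.
- **Nausea/vomiting/diarrhea row of Table 6, Grade 4:** "Permanently discontinue patient from APR-246".

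Table 6 is headed "Recommendations for APR-246 Dose Modifications and Criteria for Treatment Interruption and Re-Initiation with Treatment-Related Adverse Events", so like the stop rule it concerns treatment-related events. QTc prolongation has no row in Table 6 but has its own rule earlier in 6.2.1.

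**The concern.** A site that sees a related Grade 4 toxicity with no row of its own can find support in 6.2.1 for stopping APR-246 permanently, for restarting one level lower, and arguably for restarting at the same dose. Two compliant sites could therefore treat the same event in opposite ways. Mucosal inflammation illustrates the kind of event meant: it has no row in Table 6, and section 2.6.5 lists it among events seen in earlier studies ("Other AEs reported in this category were pyrexia, edema, mucosal inflammation, malaise, death and disease progression"). That list gives neither grade nor attribution, so it says nothing about how often the situation will arise.

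At stake is whether a patient is re-exposed after a Grade 4 related toxicity. The summary of adverse events leading to early discontinuation of study drug (section 9.3.3) could also depend on which reading each site adopts.

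**Working it through.** The plan states no figure for this point, so the check sets the instructions side by side. The only arithmetic is the dose under each reading.

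**1. Scope.** Treatment-related, non-haematologic, Grade 4, no named row in Table 6, not QTc, not among the listed exceptions.

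**2. What each instruction gives for such an event, starting from 4.5 g/day.**

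| Instruction in 6.2.1 | Action | Daily dose |
|---|---|---|
| Stop rule | Permanent discontinuation | 0 g |
| Last row of Table 6 | Hold to Grade 1 or less, then one level down | 4.0 g |
| Reduction sentence | Lower dose from the next cycle | 4.0 g |
| Same-dose sentence | Resume after recovery | 4.5 g |

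**3. Does the proviso in the stop rule rank them?** Table 6 has 7 non-haematologic Grade 4 entries. Six named rows stop the drug: creatinine, bilirubin, AST/ALT, CNS, infusion related reaction, and nausea/vomiting/diarrhea. One, the last row, restarts it (6 + 1 = 7).

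- If the last row is the case specified elsewhere, the stop rule mostly repeats the six named rows, and the electrolyte exception is unnecessary because every unnamed Grade 4 event could restart anyway.
- If the stop rule prevails, the last row's reference to Grade 4 covers only exceptions without a row of their own, such as correctable electrolyte imbalances. The row does not limit itself in that way.
- The paragraph's pointer to the tables is not in the Grade 4 sentence. It comes later, in the sentence on prolonged interruptions and Grade 3 events: "a Grade 3 adverse event will decrease the dose of study drug after their recovery (see specific tables for dose adjustment guidelines".

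**4. Do the other two sentences settle it?** The reduction sentence favours restart, because lowering a later dose presupposes that there is one. Read literally, though, it also covers Grade 4 creatinine or bilirubin, which Table 6 stops, so it cannot serve as a ranking rule. The same-dose sentence gives a third outcome and carries its own proviso. Neither says which instruction yields.

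**5. Size of the difference.** Inputs are Table 5 and its footnote, with four infusion days per cycle.

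- Starting dose: 4 × 4.5 = 18 g per cycle.
- One level down: 4.0/4.5 = 0.889, a reduction of about 11%; 4 × 4.0 = 16 g per cycle. The footnote gives an average Cmax 19% lower.
- Two levels down, if the patient was already at 4.0 g: 3.5/4.5 = 0.778, a reduction of about 22%; 4 × 3.5 = 14 g per cycle. The footnote gives an average Cmax 33% lower and requires prior discussion with the Sponsor and Medical Monitor.
- Stop: 0 g.
- At 3.5 g, stopping and reducing one level coincide, because a patient needing more than two reductions is discontinued permanently (absent re-escalation).

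**6. Nausea, vomiting and diarrhea.** The text exempts cases controllable by medication from the stop rule. The Grade 4 row has no such exemption. This mismatch does not depend on how the proviso is read.

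**7. Section 6.2.2 (secondary).** For Grade 3 or higher events that resolve, it says that "within 2 hours, the infusion may be resumed at the same infusion rate", and it recommends dose reduction after CNS events of Grade 3 or higher. Both wordings include Grade 4, where the CNS row of Table 6 stops the drug.

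**The case against.** The strongest defence is that the text can be read coherently. The stop rule yields to cases specified elsewhere, Table 6 in the same section specifies otherwise for unnamed toxicities, and the reduction sentence repeats that result. On this reading the redundancy in step 3 proves little, since general rules often restate specific ones and the stop rule still adds that recovery time is irrelevant. This is a fair reading, and redundancy alone does not show a conflict.

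It is not the only fair reading. Table 6 is labelled as recommendations while the stop rule is worded as mandatory, which points the other way. With good textual arguments on both sides, what stands is that precedence is not stated.

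The safeguards are also real:

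- A life-threatening event is serious (8.1.2.4), is reported within one business day (8.1.2.6) and is reviewed by the medical monitor (8.1.2.7).
- Section 5.4 requires discontinuation once the investigator judges that toxicity precludes further therapy. The synopsis requires it for an adverse experience that makes continued participation an unacceptable risk.
- The line closing Table 6 asks for clinical judgment and allows consultation with the Medical Monitor.

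These lower the chance of unreviewed re-exposure. None says which dosing rule applies.

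A reader might go further and infer that the protocol directs rechallenge after life-threatening toxicity. The documents do not support that: the stop rule is there and may well be the one intended. Nor does 6.2.2 show that Grade 4 CNS events may be rechallenged, since the CNS row and the stop rule's disregard of recovery time suggest that the stop governs.

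**Conclusion.** The point holds as an inconsistency in stated dosing rules. For the scope in step 1, section 6.2.1 supports different actions without ranking them, and the nausea/vomiting/diarrhea row contradicts the text's exception. From the starting dose the readings span 0 to 4.5 g/day, with 4.0 g/day under the last row of Table 6. This assumes that the stop rule refers to APR-246, the subject of the section, although the sentence does not name the drug.

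The practical effect is limited to dosing safety and possibly the counts of events leading to discontinuation. Its size cannot be estimated because no Grade 4 frequency is given. A reader might infer damage to the primary comparison, but these rules do not enter the CR definition or its test, so there is no direct effect. Severity: a minor to moderate wording correction. Confidence is high that precedence is unstated; it does not extend to the practical impact.

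**What to change.** Choose one rule and state it in both the text of 6.2.1 and Table 6.

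**Default (stop after Grade 4):**
- Split the last row of Table 6. Grade 3: delay to Grade 1 or less, then reduce one level. Grade 4: discontinue APR-246 permanently, except for the exceptions listed in the text.
- Limit the reduction sentence to Grade 3 events and to Grade 4 events that are haematologic or among those exceptions.
- Exclude Grade 4 from the same-dose sentence.

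**If restart is intended:** say in the text of 6.2.1 that the last row of Table 6 is the case the proviso refers to. Also exclude Grade 4 from the same-dose sentence, so that the third outcome disappears.

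**In either case:** add to the Grade 4 nausea/vomiting/diarrhea row that it does not apply when the event is controlled by medication.

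**Optional:** exclude Grade 4 from the resumption and dose-reduction sentences of 6.2.2, to match the CNS row.

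Under the default the cost is a wording amendment to two Table 6 rows and two sentences of 6.2.1, plus two sentences of 6.2.2 if the optional change is made. It adds no visits, tests or patients.
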